8.1.1.2 Ipilimumab Dose Discontinuation for Cohorts A, B, and C

Ipilimumab must be permanently discontinued if any of the following criteria are met:

- Any Grade 2 drug-related uveitis or eye pain or blurred vision that does not respond to topical therapy and does not improve to Grade 1 severity within 2 weeks OR requires systemic treatment;
- Any Grade ≥ 3 bronchospasm or other hypersensitivity reaction;
- Any other Grade 3 non-skin, drug-related adverse event with the following exceptions for laboratory abnormalities, grade 3 nausea and vomiting, grade 3 neutropenia and thrombocytopenia, and symptomatic endocrinopathies (except for adrenal insufficiency) which resolved (with or without hormone substitution);
- Any drug-related LFT abnormality that meets the following criteria require discontinuation:
 - AST or ALT $> 8x$ ULN
 - Total bilirubin $> 5 x$ ULN
 - Concurrent AST or ALT $> 3 x$ ULN and total bilirubin $> 2 x$ ULN
- Any Grade 4 drug-related AE or laboratory abnormality, except for the following events, which do not require discontinuation:
 - Grade 4 neutropenia ≤ 7 days
 - Grade 4 lymphopenia or leukopenia
 - Isolated Grade 4 amylase or lipase abnormalities which are not associated with symptoms or clinical manifestations of pancreatitis. The BMS Medical Monitor should be consulted for Grade 4 amylase or lipase abnormalities.
 - Isolated Grade 4 electrolyte imbalances/abnormalities that are not associated with clinical sequelae and are corrected with supplementation/appropriate management within 72 hours of their onset
 - Grade 4 drug-related endocrinopathy AEs such as hyper- or hypothyroidism, or glucose intolerance, which resolve or are adequately controlled with physiologic hormone

replacement (corticosteroids, thyroid hormones) or glucose controlling agents, respectively, may not require discontinuation after discussion with and approval from the BMS Medical Monitor.

- Any treatment delay resulting in no ipilimumab dosing for > 12 weeks with the following exceptions: Dosing delays to manage drug-related AEs, such as prolonged steroid tapers, are allowed. Prior to re-initiating treatment in a participant with a dosing delay lasting > 12 weeks, the BMS medical monitor must be consulted. Tumor assessments should continue as per protocol even if dosing is delayed.
- Dosing delays resulting in no ipilimumab dosing for > 12 weeks that occur for non-drug-related reasons may be allowed if approved by the BMS medical monitor. Prior to re-initiating treatment in a participant with a dosing delay lasting > 12 weeks, the BMS medical monitor must be consulted. Tumor assessments should continue as per protocol even if dosing is delayed.
- Any AE, laboratory abnormality, or intercurrent illness which, in the judgment of the Investigator, presents a substantial clinical risk to the participant with continued ipilimumab dosing.

8.1.1.3 Nivolumab and Ipilimumab Dose Discontinuation for Special Population (Cohort A1)

The dose discontinuation criteria described in [Section 8.1.1.1](#) and [Section 8.1.1.2](#) apply to special population participants, with the following exceptions for hepatic impairment:

- Any liver function test (LFT) abnormality that meets the following criteria require discontinuation (also see Hepatic Adverse Event Management Algorithm):
 - AST or ALT > 10 x ULN for > 2 weeks
 - AST or ALT > 15 x ULN
 - Total bilirubin > 8 x ULN
 - Concurrent AST or ALT > 3 x ULN and total bilirubin > 5 x ULN
- Any drug-related renal dysfunction

Participants requiring renal transplant must be discontinued from study therapy. In some cases, participants requiring dialysis may be permitted to continue study therapy; however, these cases must be reviewed and approved by the BMS Medical Monitor.

8.1.2 Disease Progression

In general, study treatment must be discontinued at the time of disease progression per Response Evaluation Criteria in Solid Tumors (RECIST 1.1) criteria. However, accumulating evidence indicates a minority of participants treated with immunotherapy may derive clinical benefit despite initial evidence of progressive disease.³⁶

Participants may be permitted to continue study treatment with nivolumab (with or without ipilimumab) beyond initial RECIST 1.1 defined progressive disease, assessed by the investigator

up to a maximum of 24 months from date of first dose, upon approval by the BMS Medical Monitor or Study Director, as long as they meet the following criteria:

- Investigator-assessed clinical benefit.
- Tolerance of study drug
- Stable performance status
- Treatment beyond progression will not delay an imminent intervention to prevent serious complications of disease progression (eg, CNS metastases)
- Participant provides written informed consent prior to receiving additional nivolumab treatment. All other elements of the main consent including description of reasonably foreseeable risks or discomforts, or other alternative treatment options will still apply.

A radiographic assessment/ scan should be performed within 6 weeks of initial investigator-assessed progression to determine whether there has been a decrease in the tumor size or continued progressive disease. The assessment of clinical benefit should be balanced by clinical judgment as to whether the participant is clinically deteriorating and unlikely to receive any benefit from continued treatment with nivolumab.

If the investigator feels that the nivolumab participant continues to achieve clinical benefit by continuing treatment, the participant should remain on the trial and continue to receive monitoring according to the Schedule of Activities in [Section 2](#).

For the participants who continue nivolumab study therapy beyond progression, further progression is defined as an additional 10% increase in tumor burden with a minimum 5 mm absolute increase from time of initial progressive disease. This includes an increase in the sum of diameters of all target lesions and/ or the diameters of new measurable lesions compared to the time of initial progressive disease. Nivolumab treatment should be discontinued permanently upon documentation of further progression.

New lesions are considered measureable at the time of initial progression if the longest diameter is at least 10 mm (except for pathological lymph nodes which must have a short axis of at least 15 mm). Any new lesion considered non-measureable at the time of initial progression may become measureable and therefore included in the tumor burden if the longest diameter increases to at least 10 mm (except for pathological lymph nodes which must have a short axis of at least 15 mm). In situations where the relative increase in total tumor burden by 10% is solely due to inclusion of new lesions which become measurable, these new lesions must demonstrate an absolute increase of at least 5 mm.

8.1.3 Additional Guidance on Treatment Discontinuation

Discontinuation of the study treatment for abnormal liver tests should be considered by the investigator when a participant meets one of the conditions outlined in [Section 7.4.1](#) OR [Appendix 7](#) or if the investigator believes that it is in best interest of the participant. Discontinuation is required if the participants meets one of the conditions described in [Section 8.1](#).

Refer to the Schedule of Activities for data to be collected at the time of treatment discontinuation and follow-up and for any further evaluations that can be completed

In the case of pregnancy, the investigator must immediately notify the BMS Medical Monitor/designee of this event. In the event a normal healthy female participant becomes pregnant during a clinical trial, the study treatment must be discontinued immediately. In most cases, the study treatment will be permanently discontinued in an appropriate manner (eg, dose tapering if necessary for participant safety). Please call the BMS Medical Monitor within 24 hours of awareness of the pregnancy. If the investigator determines a possible favorable benefit/risk ratio that warrants continuation of study treatment, a discussion between the investigator and the BMS Medical Monitor/designee must occur.

All participants who discontinue study treatment should comply with protocol specified follow-up procedures as outlined in [Section 2](#). The only exception to this requirement is when a participant withdraws consent for all study procedures including post-treatment study follow-up or loses the ability to consent freely (ie, is imprisoned or involuntarily incarcerated for the treatment of either a psychiatric or physical illness).

If study treatment is discontinued prior to the participant's completion of the study, the reason for the discontinuation must be documented in the participant's medical records and entered on the appropriate case report form (CRF) page.

8.1.4 Post Study Treatment Study Follow-up

In this study, overall survival is a key secondary endpoint of the study. Post study follow-up is of critical importance and is essential to preserving participant safety and the integrity of the study. Participants who discontinue study treatment must continue to be followed for collection of outcome and/or survival follow-up data as required and in line with [Section 5](#) until death or the conclusion of the study.

8.2 Discontinuation from the Study

Participants who request to discontinue study treatment will remain in the study and must continue to be followed for protocol specified follow-up procedures. The only exception to this is when a participant specifically withdraws consent for any further contact with him/her or persons previously authorized by participant to provide this information.

- Participants should notify the investigator of the decision to withdraw consent from future follow-up **in writing**, whenever possible.
- The withdrawal of consent should be explained in detail in the medical records by the investigator, as to whether the withdrawal is from further treatment with study treatment only or also from study procedures and/or post treatment study follow-up, and entered on the appropriate CRF page.
- In the event that vital status (whether the participant is alive or dead) is being measured, publicly available information should be used to determine vital status only as appropriately directed in accordance with local law.

- If the participant withdraws consent for disclosure of future information, the sponsor may retain and continue to use any data collected before such a withdrawal of consent.

8.3 Lost to Follow-Up

- All reasonable efforts must be made to locate participants to determine and report their ongoing status. This includes follow-up with persons authorized by the participant.
- Lost to follow-up is defined by the inability to reach the participant after a minimum of **three** documented phone calls, faxes, or emails as well as lack of response by participant to one registered mail letter. All attempts should be documented in the participant's medical records.
- If it is determined that the participant has died, the site will use permissible local methods to obtain date and cause of death.
- If investigator's use of third-party representative to assist in the follow-up portion of the study has been included in the participant's informed consent, then the investigator may use a Sponsor retained third-party representative to assist site staff with obtaining participant's contact information or other public vital status data necessary to complete the follow-up portion of the study.
- The site staff and representative will consult publicly available sources, such as public health registries and databases, in order to obtain updated contact information.
- If after all attempts, the participant remains lost to follow-up, then the last known alive date as determined by the investigator should be reported and documented in the participant's medical records.

9 STUDY ASSESSMENTS AND PROCEDURES

- Study procedures and timing are summarized in the Schedule of Activities ([Section 2](#)).
- Protocol waivers or exemptions are not allowed.
- All immediate safety concerns must be discussed with the Sponsor immediately upon occurrence or awareness to determine if the participant should continue or discontinue treatment.
- Adherence to the study design requirements, including those specified in the Schedule of Activities, is essential and required for study conduct.
- All screening evaluations must be completed and reviewed to confirm that potential participants meet all eligibility criteria before treatment assignment. The investigator will maintain a screening log to record details of all participants screened and to confirm eligibility or record reasons for screening failure, as applicable.
- Procedures conducted as part of the participant's routine clinical management (eg, blood count) and obtained before signing of informed consent may be utilized for screening or baseline purposes provided the procedure meets the protocol-defined criteria and has been performed within the timeframe defined in the Schedule of Activities.

Additional measures beyond those described in [Section 2](#), including non-study required laboratory tests, should be performed as clinically indicated or to comply with local regulations. Laboratory toxicities (eg, suspected drug induced liver enzyme evaluations) will be monitored during the follow-up phase via on site/local labs until all study drug related toxicities resolve, return to baseline, or are deemed irreversible.

If a participant shows pulmonary-related signs (hypoxia, fever) or symptoms (eg, dyspnea, cough, fever) consistent with possible pulmonary AEs, the participant should be immediately evaluated to rule out pulmonary toxicity, according to the suspected pulmonary toxicity management algorithm in the BMS-936558 (nivolumab) Investigator Brochure and [Appendix 7](#).

Some of the assessments referred to in this protocol may not be captured as data in the eCRF. They are intended to be used as safety monitoring by the treating physician. Additional testing or assessments may be performed as clinically necessary or where required by institutional or local regulations.

9.1 Efficacy Assessments

Overall survival is one of the secondary endpoints in the study. Every effort will be made to collect survival data on all participants including participants withdrawn from treatment for any reason, who are eligible to participate in the study and who have not withdrawn consent for survival data collection. If the death of a participant is not reported, all dates in this study representing a date of participant contact will be used in determination of the participant's last known date alive.

Study evaluations will take place in accordance with the Schedule of Activities (Section 2), according to RECIST 1.1 criteria.⁵¹ CT with oral/IV contrast or contrast-enhanced MRI is the preferred imaging modalities for assessing radiographic tumor response. If a participant has a known allergy to contrast material, please use local prophylaxis standards to obtain the assessment with contrast if at all possible, or use the alternate modality. In cases where contrast is strictly contraindicated, a non-contrast scan will suffice. Screening assessments should be performed within 42 days of start of study treatment. Brain MRI is the preferred imaging method for evaluating CNS metastasis, and assessment is required during screening in participants with a known history of treated brain metastases. All known or suspected sites of disease (including CNS) should be assessed at screening and at subsequent assessments using the same imaging method and technique. If more than one method is used at screening, then the most accurate method according to RECIST 1.1 should be used when recording data, and should again be used for all subsequent assessments. Bone scan, positron emission tomography (PET) scan, or ultrasound are not adequate for assessment of RECIST response. In selected circumstances where such modalities are the sole modality used to assess certain non-target organs, those non-target organs may be evaluated less frequently. For example, bone scans may need to be repeated only when complete response is identified in target disease or when progression in bone is suspected. Previously treated CNS metastases are not considered measurable lesions for purposes of RECIST determined response. Participants with a history of brain metastasis should have surveillance MRI approximately every 12 weeks, or sooner if clinically indicated.

Radiographic tumor assessments will be conducted until disease progression (or until discontinuation of study therapy in participants receiving study drug beyond progression), lost to follow-up, or withdrawal of study consent. Tumor assessments for all participants should continue as per protocol even if dosing is interrupted. Tumor measurements should be made by the same investigator or radiologist for each assessment whenever possible. Changes in tumor measurements and tumor responses to guide ongoing study treatment decisions will be assessed by the investigator using RECIST 1.1 ([Appendix 6](#)).

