| Radiographic Tumor Assessments(chest, abdomen, pelvis, brain) | X | Section 9.1.1, Appendix 6 Performed within 28 days prior to first dose. CT with IV contrast of Chest, Abdomen, Pelvis and all known or suspected sites of disease should be imaged at the screening visit. MRI with gadolinium may be obtained if CT iodinated contrast is contraindicated. MRI of brain without and with gadolinium is required for all participants during screening to rule out brain metastases. CT of the brain (without and with contrast) can be performed if MRI is contraindicated. See Section 9.1 for further details |
| Biomarker Assessments | | |
| Archived Tumor Tissue or Recent Tumor Biopsy | X | Section 9.8.1 For Cohorts A, A1, and B: Fresh or archival sample, obtained within 12 months prior to enrollment. If archived slides are to be submitted, they must not have been cut > 6 months prior to submission, as sample may have degraded. One formalin-fixed paraffin embedded tumor tissue block or a minimum of 10 to 15 unstained tumor tissue sections are acceptable. For Cohort C: 
 • Fresh or archival sample, obtained within 3 months prior to enrollment. • Submission of 10 unstained tumor tissue sections for TMB testing by Foundation Medicine unless TMB results from Foundation Medicine is already available (Note: participants may not enter treatment phase unless known results are TMB high) Submission of 5 additional slides for PD-L1 testing if results are not already available from another BMS study, or a commercially available complementary diagnostic using an acceptable antibody (ie, 28-8, 22-C3, SP263). PD-L1 results obtained using antibody SP142 are not acceptable. |

Table 2-1: Screening Procedural Outline (CA209817)

| Procedure | Screening Visit (≤ 42 days) | Notes |
|--|--------------------------------|--|
| | | |
| EGFR Mutation and ALK Translocation Statuses | X | To be performed for all non-squamous participants (unless harboring known KRAS mutation). EGFR and ALK tests may be performed locally or at a central laboratory. May be performed outside the Screening period window, eg, > 42 days prior to first dose. |
| IVRS /Clinical Drug Supplies | | |
| IRT | X | Section 7.2 For participant number assignment at the time informed consent is obtained |

Table 2-2: Treatment Phase Assessments (CA209817)

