APPENDIX 11 REVISED PROTOCOL SUMMARY OF CHANGE HISTORY

Overall Rationale for the Revised Protocol 05, 04-Jun-2018

The study protocol has been updated to include safety as the primary endpoint for Cohort C aligning with the primary objective of the study. Additional changes updated document to align with current program standards.

| SUMMARY OF KEY CHANGES OF REVISED PROTOCOL 05 | | |
|---|---|---|
| Section Number & Title | Description of Change | Brief Rationale |
| Title Page | Updated study personnel | To update study personnel |
| Section 1 Synopsis Table 4-1 Objectives and Endpoints Figure 5.1-1 CA209817 Study Design Schema Section 10.3.1 Efficacy Analyses and Section 10.3.2 Safety Analyses | Modified objectives and endpoints for Cohort C | To include safety as the primary endpoint for Cohort C |
| Section 1 Synopsis Figure 5.1-1 CA209817 Study Design Schema Section 5.2.1 All Cohorts (NSCLC) Section 10.1 Sample Size Determination [REDACTED] | Modified cohort size for Cohort C | To include safety as the primary endpoint for Cohort C |
| [REDACTED] | | |
| Table 2-1 Screening Procedural Outline Section 6.2 Exclusion Criteria | Updated language for EGFR mutation and ALK testing requirements | To provide clarity for sites that test results from either local and/or central laboratories are acceptable |
| Table 2-1 Screening Procedural Outline Table 2-2 Treatment Phase Assessments | Updated radiographic assessments for brain metastases | To clarify inconsistency in the MRI requirements versus preferred modality for the brain scans |
| Section 5.5.5 Rationale for Tumor Mutation Burden Testing | Modified document with updated CA209227 study results | To update document with study results |
| Section 6.2 Exclusion Criteria 3)c Section 7.7.1 Prohibited and/or Restricted Treatments | Allowed marijuana use by prescription or by local legal status | Allowed marijuana use for treatment of cancer/cancer treatment symptoms |
| Section 7.1 Treatments Administered | Updated treatment procedures | To provide clarity on infusion steps |

SUMMARY OF KEY CHANGES OF REVISED PROTOCOL 05

| Section Number & Title | Description of Change | Brief Rationale |
|--|--|--|
| Section 7.4.4 Management Algorithms for Immuno-Oncology Agents | Added monitoring for myotoxicity | [REDACTED] |

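### Does Section 9.1 restrict screening brain imaging to participants with treated brain metastases, against Table 2-1?

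*Combined protocol and SAP*

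**What the plan says.** Two places in the protocol address brain imaging at screening.

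- **Table 2-1 (Section 2, Schedule of Activities), radiographic tumor assessment row:** "MRI of brain without and with gadolinium is required for all participants during screening to rule out brain metastases". The row continues: "CT of the brain (without and with contrast) can be performed if MRI is contraindicated. See Section 9.1 for further details".
- **Section 9.1, Efficacy Assessments:** after naming MRI as the preferred method for the brain, the text says "assessment is required during screening in participants with a known history of treated brain metastases". The next sentence adds: "All known or suspected sites of disease (including CNS) should be assessed at screening".

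Two further places bear on which text controls. Earlier in the same Section 9.1 paragraph, the protocol states "Study evaluations will take place in accordance with the Schedule of Activities (Section 2"). The introductory list of Section 9 says "Adherence to the study design requirements, including those specified in the Schedule of Activities, is essential and required for study conduct", and "All screening evaluations must be completed and reviewed to confirm that potential participants meet all eligibility criteria before treatment assignment". That list also rules out waivers.

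**The concern.** The table's imaging row ends by pointing to Section 9.1. A reader who follows the pointer finds a requirement worded for people whose brain metastases are already known and treated, widened by the next sentence to known or suspected CNS disease. That is still not everyone. Section 9.1.1 does not help, because it deals only with possible independent review of scans.

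Baseline brain status matters for entry. Exclusion 2a in Section 6.2 bars untreated CNS metastases, while Section 6.1.1 makes untreated, asymptomatic brain metastases one route into Cohort A1. The participants for whom a screening scan settles these questions are those with untreated and possibly unsuspected lesions, and the Section 9.1 sentence does not mention them. A site that worked from that sentence alone could place such a person in a cohort that excludes them.

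**Working it through.** No formula or planned figure is involved. The check is whether the two statements can both be obeyed and, if a reader is in doubt, which one the protocol makes binding.

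**1. The groups.** Let S be everyone screened, T those with brain metastases known and already treated, and K those with known or suspected CNS disease.

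| Source | Imaging required in | Anyone exempted? |
|---|---|---|
| Table 2-1 | S | No; CT replaces MRI if MRI is contraindicated |
| Section 9.1 | T, and K by the next sentence | No |

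**2. Joint compliance.** T and K both lie inside S, so the group to be imaged under both texts is S ∪ T ∪ K = S. Participants left without a scan when both are followed: S minus S, which is 0. A true contradiction would need Section 9.1 to say that imaging is required *only* in T or K, or is not needed elsewhere. It says neither. A requirement stated for part of a group does not cancel one stated for the whole group.

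**3. Which text controls.** The Section 9.1 paragraph places itself under the Schedule of Activities ("Study evaluations will take place in accordance with the Schedule of Activities (Section 2"). Section 9 makes adherence to the Schedule compulsory and requires all screening evaluations to be finished and reviewed before treatment assignment. The table's brain-imaging line is one of those evaluations, and it states its purpose, which is to exclude brain metastases. A site unsure after reading Section 9.1 is therefore sent back to the table, and the table covers everyone.

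**4. A sensible reading of the narrower sentence.** The rest of the paragraph concerns keeping the same imaging method over time, not counting previously treated CNS lesions as measurable, and surveillance MRI about every 12 weeks in participants with a history of brain metastasis. In that setting, singling out participants with treated metastases reads naturally as a reminder that they need a baseline for later comparison. This is an inference from context. Steps 2 and 3 do not depend on it.

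**5. Effect on the analysis.** Section 3.1.1 states that there is no formal hypothesis and that the analyses are descriptive. No sample size, estimate or test uses the Section 9.1 sentence.

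**The case for a change.** The strongest case for a change is that an order of precedence helps a careful site but does not make two texts agree. The deference to the Schedule is general, whereas the pointer from Table 2-1 to Section 9.1 is specific to imaging. If everyone is to be scanned, naming one subgroup is redundant at best and could be taken as a limit. The assessment decides eligibility, and the edit would cost one sentence. The argument can be extended: Appendix 6 counts brain metastases first found on study as progression even without a baseline brain scan, so a missed lesion could later be recorded as a PFS event.

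Part of this stands. The wordings differ, and the section cited for details is the less complete of the two. The consequences do not follow from the plan, however. Each needs a site to pass over an explicit all-participant line in the screening table, disregard the opening of Section 9, and act on one sentence in an efficacy section. Even then, suspected CNS disease would still be imaged under Section 9.1 itself, which leaves only unsuspected lesions at a site already deviating from protocol. The Appendix 6 rule adds nothing until that deviation has happened.

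Nor is the 42-day figure in the same paragraph a second discrepancy. It is the general screening window in the heading of Table 2-1, while the 28-day limit for tumor imaging is set in that table and again in inclusion criterion 2d.

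**Conclusion.** The concern does not hold as a reason to change the plan. Section 9.1 is incompletely worded, but it is compatible with Table 2-1, and the protocol itself says the Schedule of Activities is to be followed. The number of participants affected is 0 when Table 2-1 is applied. The number at a site that ignored the table cannot be derived, because the documents give neither a rate of unsuspected brain metastases nor a rate of such deviations.

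This rests on two assumptions: that sites treat the Schedule as binding, as Section 9 instructs, and that a requirement stated for a subgroup is not read as releasing everyone else. Bringing the sentence into line with the table would be reasonable tidying if the paragraph were being revised for another reason. By itself it would alter no scan, cohort assignment or reported result.
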